5.5 Methods for withdrawals, loss to follow-up and Missing Data

We will not have withdrawals nor loss to follow-up since this is a survey cross-sectional design. However, participants selected for the sample may not be present when we visit the household the first time, in which case we will carry out up to two more call backs. In the case where field call backs and tracing have not been successful to ensure all key data have been collected, multiple imputation methods will be used to generate outcomes. For example, blood pressure level might be missing for some cases. We will conduct a complete case analysis and also an analysis where missing blood pressure levels are imputed (imputed analysis) and compare whether there are apparent variations in the results obtained. The same applies for other key variables like self-reported hypertension.

Multiple imputation methods for cluster randomised trials with few clusters are not well developed, although this is a growing research field. A systematic review done recently showed none of the studies reviewed had a multiple imputation procedure that handled clustering and very few techniques also used these in regression models that truly adjusted for the clustering effect⁷. We intend to implement some of these procedures in our analysis as part of sensitivity analysis, but the main analysis will be based on the complete cases.

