6.5 Other analysis supporting the primary analysis (including sensitivity analyses)

Apart from looking at the observed effect of the intervention, a sensitivity analysis will be conducted:

- 1. The primary analysis on hypertensive drugs described in section 5.7 excludes from the analysis those who do not name any specific drugs we will include these in a sensitivity analysis.
- 2. We will undertake sensitivity with individuals analyzed in the "last" clinic that they attended.
- 3. We will adjust for potential confounding factors using the two stage regression model¹³. Firstly, two logistic regression models for control and intervention clinics that include covariates will be fitted separately, with individual level covariates such as gender and age. Secondly, based on residuals from the first stage we will aggregate outcomes to cluster level and cluster/clinic level factors (e.g. clinic size) will be used in regression modeling at the cluster level to test the effect of the intervention.
- 4. In order to compare the results from the two stage regression an alternative procedure will be used, the mixed effects model adjusting for covariates.

Model sensitivity to the individual-level data will be assessed on different temporal covariance structures (exchangeable, auto covariance and unstructured) on the final model. Such assessment will be made possible because of the many appointments with the 21 months of follow-up.

Thus, endeavors to ensure data are complete will be explored rigorously taking advantage of this longitudinal nature of data and, in the process a report for missing data

by variable will be compiled. This will help to classify the missing data as either missing at random (MAR) or missing not at random (MNAR). Assuming the data are MAR the proposed mixed logistic models should sufficiently handle these. If otherwise, as with MNAR we will employ data imputation procedures accordingly, taking caution not to distort the patterns observed from the data. However, as this is an area in which research is ongoing, this will be an exploratory analysis, not reported in the main trial report, and drawing on latest research. The dummy tables for these and details on how imputation on clustered data will be done, will not be provided in this analysis plan.

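### Section 6.5 chooses the missing-data method by classifying data as MAR or MNAR, which observed data cannot do, names no MNAR method, and appears to keep out of the main report the imputed check planned in 5.5

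*SAP*

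**What the plan says.** Section 5.5 makes complete cases the main analysis and adds an imputed one for comparison: "We will conduct a complete case analysis and also an analysis where missing blood pressure levels are imputed (imputed analysis". It extends this to other key variables such as self-reported hypertension, calls it a sensitivity analysis, and admits that imputation methods for few clusters are not well developed. Section 5.6 also plans multiple imputation that allows for clustering, in connection with outliers.

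Section 6.5, on analyses supporting the primary analysis, sets a different procedure. A missing-data report by variable is to be compiled, making use of what the section calls the longitudinal nature of the data. Of this report it says: "This will help to classify the missing data as either missing at random (MAR) or missing not at random (MNAR". Two branches follow:

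- MAR: "Assuming the data are MAR the proposed mixed logistic models should sufficiently handle these".
- MNAR: "If otherwise, as with MNAR we will employ data imputation procedures accordingly".

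It then states that "this will be an exploratory analysis, not reported in the main trial report, and drawing on latest research", and that "details on how imputation on clustered data will be done, will not be provided in this analysis plan".

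**The concern.** A procedure that depends on knowing whether data are MAR or MNAR needs information the data do not contain. A missing-data report can show that missingness varies with age, sex or clinic, which is evidence against data being missing completely at random. It cannot show whether, among people alike on everything recorded, those with missing blood pressure had higher or lower values.

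The MNAR branch then offers imputation without saying what departure from MAR it would encode. An analyst who used standard multiple imputation there would be making the MAR assumption just rejected.

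Also at stake is whether readers of the main paper see any check on the complete-case result. Section 5.5 points one way and 6.5 another, and no imputation model is given anywhere. The SAP is dated 6 April 2016 and the follow-up survey ran from September to November 2015 (4.3), so the method would be chosen after the data had been collected.

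**Working it through.** **1. The SAP's only figure on missingness.** Section 5.11 gives 3905 responses from 4903 sampled. 3905/4903 = 0.7965, which agrees with the stated 79.6%; non-response is 20.4%. This is non-response of whole people. The SAP gives no rate of missing blood pressure among those interviewed.

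**2. The sections side by side.**

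| Question | 5.5 | 6.5 |
|---|---|---|
| Is imputation done? | Yes, for comparison with complete cases | Only if data are judged MNAR |
| Assumption | Not stated | Offered for MNAR; no delta shift, pattern-mixture or selection model named |
| Reported? | Sensitivity analysis; place not stated | Not in the main report |
| Details | None | Expressly left out |

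Section 4.2 says the follow-up survey uses a different sample, so nobody has a repeated primary outcome for a longitudinal model to draw on. Repeated appointments exist only in the clinic link data (4.5, 5.8).

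**3. Why the mechanism cannot be read from the data.** Let m be the share missing, and p_obs and p_mis the prevalence in observed and missing people with the same covariates.

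True prevalence = (1 − m) × p_obs + m × p_mis

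Truth minus complete-case (or MAR-based) estimate = m × (p_mis − p_obs)

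The quantity p_mis is never observed, and MAR and MNAR differ only in it. Take p_obs = 36% (the background prevalence in 3.5) and, as an assumption, p_mis = 50%:

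- m = 5%: 0.95 × 0.36 + 0.05 × 0.50 = 0.367, so the estimate is 0.7 points too low.
- m = 10%: 0.90 × 0.36 + 0.10 × 0.50 = 0.374, so it is 1.4 points too low.

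With the odds ratio of outcome, missing versus observed, assumed to lie between 0.5 and 3 (p_mis from 22.0% to 62.8%):

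| m (assumed) | Truth minus estimate, points |
|---|---|
| 2% | −0.3 to +0.5 |
| 5% | −0.7 to +1.3 |
| 10% | −1.4 to +2.7 |
| 20.4% (all non-response counted as missing) | −2.9 to +5.5 |

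If 5% were missing in one arm and 10% in the other, with p_mis = 50% in both, the spurious contrast at that survey would be 1.4 − 0.7 = 0.7 points. The primary outcome is change between surveys, so an imbalance that stayed the same would largely cancel.

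**4. What MAR-based imputation does under each mechanism.** An invented example: two equal age groups with prevalence 55% and 20% (truth 37.5%), and 20% missing overall.

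- MAR, with 10% missing in the older and 30% in the younger group. Complete case: (0.5 × 0.9 × 0.55 + 0.5 × 0.7 × 0.20)/0.8 = 39.7%. Imputation within age group recovers 37.5%.
- MNAR, with 30% missing among people with the outcome and 14% among those without. Complete case: 0.375 × 0.70/(0.375 × 0.70 + 0.625 × 0.86) = 32.8%. Imputation within age group: older 0.385/0.772 = 49.9%, younger 0.140/0.828 = 16.9%, average 33.4%.

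A simulation of 400,000 people agreed within sampling error (truth 37.6%; MAR-based imputation 37.6% under MAR and 33.6% under MNAR). MAR-based imputation corrects the first mechanism and leaves most of the bias under the second.

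**5. Which missing values reach the complete-case outcome.** In Appendix C, missing cholesterol gives 0 for dyslipidaemia, and missing glucose gives 0 on the glucose criterion for diabetes. Missing waist gives 1, because that line has no guard and Stata treats missing as larger than any number. Missing blood pressure leaves the blood pressure level missing. The complete-case outcome is therefore missing mainly through blood pressure, and the other three items are filled in silently.

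**The case against.** The best defence is scope. The paragraph follows directly from remarks on temporal covariance and repeated appointments over 21 months. It could therefore govern only the clinic link data, leaving survey blood pressure to 5.5. The statement on reporting could likewise cover only the MNAR imputation, and 5.5 never says its comparison goes in the main report. These readings are possible. Against them, the section is headed as support for the primary analysis, and its last sentence refers to imputation of clustered data in general. The ambiguity stands, so this is not a flat contradiction.

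A reader might infer that 6.5 swaps the methods for MAR and MNAR. It does not: a likelihood-based mixed model is valid when the outcome is MAR given the model's covariates. A reader might also infer that the MNAR remedy has the same bias as complete cases. That is not established, because no remedy is fixed; delta-adjusted imputation is also an imputation procedure and could fall within the wording. Nor do people missing cholesterol, glucose or waist drop out of the complete-case analysis, as step 5 shows.

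It is also fair that the SAP claims only that the report will help to classify. The choice of method still turns on the answer.

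**Conclusion.** The point holds in this form. The classification step cannot be carried out. The MNAR branch names no method suited to MNAR, and the longitudinal premise does not apply to the primary outcome. On the natural reading, though not the only one, 6.5 keeps out of the main report the check that 5.5 plans.

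The numerical stake is probably modest. The 0.7 and 1.4 points rest on an assumed 50% prevalence among the missing and assumed missing shares of 5% and 10%. They are small beside the 11-point reduction in 3.5, and a false between-arm effect would also need missingness that differs by arm and changes between surveys. The main complete-case analysis is not invalidated. The case for change is that an unworkable rule can be replaced cheaply by a defined, reported check.

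**What to change.** 1. Delete the classify-then-choose rule and the appeal to longitudinal data from 6.5 as far as the survey outcomes are concerned. Keep complete cases as the main analysis.
2. Prespecify one multiple imputation under MAR for missing blood pressure that respects clustering. For example, impute separately by survey, with clinic, age, sex and the outcome components in the model, and derive the primary outcome afterwards.
3. Before imputing, set missing cholesterol, glucose and waist to missing in the Appendix C code, which now fills them with 0, 0 and 1. State whether the complete-case analysis keeps those fills or excludes these people, since exclusion would reduce its size.
4. Add a delta-adjusted version as the MNAR check: shift imputed blood pressure over a range stated before the clinic codes are broken, and allow the shift to differ by arm.
5. Make 5.5, 5.6 and 6.5 agree that both imputed results are reported beside the complete-case result.

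The cost is SAP wording and modest extra programming; no new data are needed. Imputation methods are less developed for trials with only eight clusters, so these should remain sensitivity analyses. The imputation model in item 2 is one defensible choice among several.

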7 ANALYSIS OF SECONDARY OUTCOMES

7.1 Secondary analysis

Secondary outcomes will be analyzed as described above for the primary outcome. They will include: proportion of population in each cluster screened (data from the population survey), adherent to medication and retained in care (from records of clinic activity). Adherence will be defined by using the records of pharmacy refills. The secondary objectives will investigate changes in proportions independently and dependently. The independent tests for proportions (Pearson's Chi-Square test) will be used for assessing between control and intervention/clusters change at the same time point.

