3 STUDY METHODS

3.1 Overall Study Design and Plan

We will conduct a cluster-randomised trial in tandem with a detailed realist evaluation. drawing on global experience of evaluating complex interventions^{1,2}. The units of randomisation will be health facilities and their surrounding catchment populations. We propose to randomise eight clinics, four of which will receive the intervention. To achieve our primary outcome, we aim to both increase the proportion of the population under active management for their hypertension and reduce the level of blood pressure in those patients already receiving care. For this reason, the outcome of the trial will be measured at population level, and we estimate that the trial has a power of above 80% to detect an 11% to 13% reduction in the proportion of the population at moderate or greater cardiovascular risk as a result of their blood pressure and other risk factors. Realist evaluation will provide data on adaption of the intervention to the context, individual and organizational processes of change as well as contextual factors that influence outcomes³. We are collecting data at two cross-sectional points 24 months apart: baseline (when intervention is introduced) and at the end of intervention at each clinic to provide data on the sustainability of the intervention. The detailed study methods are described in the following sections.

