3.5 Sample size determination

The two cross-sectional surveys, which will be used to assess the effectiveness of the intervention, will each include at least 4000 participants, giving approximately 500

people in each cluster. We adopted the use of the coefficient of variation (standard deviation of the cluster means divided by the overall mean) as used in similar study settings when we cannot get a good intra-cluster variation⁴⁻⁶. For a background prevalence of 36% (i.e. proportion of patients at moderate or greater risk of cardiovascular disease) and a coefficient of variation of 0.132 (error margin 4.5% (0.132 ± 0.045)) based on data collected in the same site in 2010, different scenarios of proportions of moderate or greater risk patients at the end of trial in the control and intervention arms and their associated power are shown in Table 1. Based on the scenario of a 15% difference (i.e. 36% in control vs 21% in intervention), the highest power will be 97.4% and we will have power of above 80% to detect an 11% absolute reduction of people at moderate or greater cardiovascular risk. These calculations assume that the coefficient of variation will be similar in the two groups and that effects of the interventions are similar across clusters.

	Control	"36%" No change	
	CV	0.132	
Intervention	"5% difference" 31%	20.7	
	"10% difference" 26%	68.6	
	"12% difference" 24%	85.4	
	"15% difference" 21%	97.4	
	Control	"34%" 2% change	
	CV	0.132	
Intervention	"3% difference" 31%	10.5	
	"8% difference" 26%	52.7	
	"10% difference" 24%	75.4	
	"13% difference" 21%	94.2	
	Control	"32%" 4% change	
	CV	0.132	
Intervention	"1% difference" 31%	4.3	
	"6% difference" 26%	35.2	
	"8% difference" 24%	58.4	
	"11% difference" 21%	87.7	

Table 1: Power	matrix of different scenari	ios
-----------------------	-----------------------------	-----

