6.3 Primary analysis

The analysis of the primary outcome (binary, as defined above) will be done in three steps Thus, firstly, a group level analysis of the overall effect of the intervention using the test of differences in two proportions (within each group at baseline and after follow-up and between intervention and control clusters) will be conducted adjusting for the design effect and clustering correction factors for each group. We will not use the usual Pearson's Chi-Square test which assumes independence as our data are clustered. Intra-class correlation (ICC) adjusted Pearson's Chi-square versions will be used as those used by Reed. These will involve creating and pilot testing a STATA program to perform these adjusted Chi-Square based analyses for binary outcome data¹⁰⁻¹².

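### SAP 7.1 contradicts itself and 6.3: it names Pearson's chi-square, with no clustering adjustment, for between-arm secondary comparisons that it also says follow the cluster-adjusted primary method

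*SAP*

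**What the plan says.** Section 3.1 sets the unit of randomisation: "We propose to randomise eight clinics, four of which will receive the intervention". Section 3.5 plans at least 4000 respondents per survey, about 500 per clinic.

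Section 6.3, on the primary outcome, is explicit: "We will not use the usual Pearson's Chi-Square test which assumes independence as our data are clustered". It prescribes versions of the chi-square adjusted for the intra-class correlation.

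Section 7.1, on the secondary outcomes, makes three statements about method:

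- The opening rule: "Secondary outcomes will be analyzed as described above for the primary outcome".
- A general remark: "The secondary objectives will investigate changes in proportions independently and dependently".
- The test for comparing arms: "The independent tests for proportions (Pearson's Chi-Square test) will be used for assessing between control and intervention/clusters change at the same time point".

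The last statement mentions no design effect, ICC or other clustering correction.

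Dummy Tables 9 and 10 (Appendix B) have columns for a within-cluster change with p-value in each arm, and a final column for a test of the difference between arms in that change.

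**The concern.** The first and third statements in 7.1 cannot both be followed as written. The first brings in the adjusted test. The third names Pearson's chi-square without the qualifier that 6.3 uses to separate the acceptable version from the excluded one. The third is also the more specific instruction, so a programmer is likely to code it.

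The ordinary test treats some 4000 respondents as independent, although only eight clinics were randomised. Differences between clinics that have nothing to do with the intervention then count as evidence of an effect. A comparison at a single time point is fully exposed to this, because stable differences between clinics do not cancel as they partly would in a comparison of changes.

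At stake are the p-values for undiagnosed hypertension, blood pressure measurement, medication use and the risk levels (Table 9, which is repeated for men and women).

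**Working it through.** **Inputs (SAP 3.1 and 3.5).** Four clinics per arm; m = 500 per clinic; p = 0.36; coefficient of variation k = 0.132, with stated margin ± 0.045, so 0.087 to 0.177. The values of p and k are for the primary outcome. Two-sided α = 0.05 is an assumption, since 3.5 gives no α. Clinics are taken as equal in size.

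**Step 1: are these inputs on the scale of the SAP's own planning?**

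ρ = k² · p₀/(1 − p₀)

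V = [p₀(1 − p₀) + p₁(1 − p₁)] · (1/m + ρ)

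Power = Φ(√3 · |p₀ − p₁| / √V − 1.96), where 3 is the number of clinics per arm less one.

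For 36% vs 26%: ρ = 0.017424 × 0.5625 = 0.0098; V = 0.4228 × 0.0118 = 0.00499; power = Φ(2.452 − 1.96) = 68.9%.

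| Control vs intervention | SAP Table 1 | Recomputed |
|---|---|---|
| 36% vs 26% | 68.6 | 68.9 |
| 36% vs 24% | 85.4 | 84.6 |
| 36% vs 21% | 97.4 | 96.7 |

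All 12 cells agree within 1.8 points. Other variants of the formula come about as close, so this does not identify the sponsor's exact calculation. It does show that the clustering assumed here is on the scale used in planning.

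**Step 2: design effect.**

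DE = 1 + (m − 1)ρ = 1 + 499 × 0.0098 = 5.89

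The unadjusted standard error is too small by a factor of √5.89 = 2.43.

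**Step 3: rejection rate of the unadjusted test under no effect.**

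Rate = 2 · [1 − Φ(1.96/√DE)] = 2 · [1 − Φ(0.808)] = 41.9%

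A beta-binomial simulation (50,000 null trials, 4 + 4 clinics of 500) gave 42.3%.

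**Step 4: sensitivity.**

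| Varied | Rejection rate at nominal 5% |
|---|---|
| k = 0.087 / 0.132 / 0.177, at p = 0.36 | 26.8% / 41.9% / 53.1% |
| p = 0.10 / 0.20 / 0.30 / 0.50 / 0.70, at k = 0.132 | 16% / 27% / 37% / 53% / 67% |
| ICC set directly: 0.001 / 0.005 / 0.01 / 0.02 | 11% / 29% / 42% / 55% |
| m = 488 (3905 baseline respondents / 8), p = 0.36, k = 0.132 | 41.5% |

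Across prevalences of 10% to 70% and the whole margin for k, the range is about 10% to 75%. No combination tried comes down to 5%.

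**Step 5: alternatives in the same simulation (p = 0.36, k = 0.132).** An ICC-adjusted chi-square with a normal reference rejects 9.6%. A clinic-level t-test on 6 degrees of freedom rejects 5.0%.

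**The case against.** The strongest reply is that the opening sentence of 7.1 governs and that Pearson is shorthand there for the adjusted version, since 6.3 also describes its method as a form of Pearson's chi-square and 7.1 never says usual or unadjusted. This reading is possible. A reader might infer that the SAP has settled on the ordinary test, and the text does not support that. But the shorthand reading is not secured either: 6.3 separates the two versions by the very qualifier that 7.1 leaves out. What remains is a contradiction that leaves the test open.

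Four further limits stand:

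- **Source of outcome (e), clinic attendance.** Section 5.7 takes it from clinic-link data, while 2.2.2 and Table 10 still describe it as self-reported. The calculation with 500 per clinic cannot simply be applied to it, nor to retention, outcome (f).
- **Test of change.** A reader might infer that none is planned. The last column of Tables 9 and 10 shows otherwise, although 7.1 covers it only through its opening sentence.
- **Dependence.** The remark on analysing changes dependently is vague, but it is not an error in itself. The two surveys sample different individuals (section 4.2), yet the same eight clinics are measured twice.
- **Confidence intervals.** Neither 7.1 nor Tables 9 and 10 promise any for these outcomes, so the point concerns p-values.

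**Conclusion.** The contradiction is real and rests on the text alone: 7.1 names, without adjustment, a test whose usual form 6.3 rules out, and it does so after adopting the 6.3 method. Followed literally, the sentence gives p-values that are too small whenever clinics differ at all in the outcome.

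The size is an illustration: about 42% false rejections at the primary outcome's planning values, 27% to 53% over the stated margin for the coefficient of variation. It would be tempting to read 42% as the error rate of each secondary test. The SAP does not support that, because it gives no prevalence, coefficient of variation or ICC for any secondary outcome. The figure applies to single-time-point comparisons of survey outcomes with about 500 respondents per clinic, and only if the unadjusted test is used. The primary analysis is not affected.

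**What to change.** Delete the Pearson sentence from 7.1 and replace it with wording such as: *Every between-arm comparison of secondary outcomes, at a single time point or as the difference in change in Tables 9 and 10, uses a method that accounts for clustering by clinic. No test that assumes independent individuals is used.*

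Preferably also name a reference distribution suited to eight clinics, for example a t-test on the change per clinic with 6 degrees of freedom. If so, call it a clinic-level method. It is not the method now written in 6.3, and describing it as the same as the primary analysis would create a new inconsistency or silently change the primary analysis.

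The minimum change is a few lines of text and needs no new data. The downside is larger p-values for the secondary outcomes, which are the correctly calibrated ones.
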